This protocol is being amended to add hepatitis serology testing at screening. For subjects who test positive for latent hepatitis B infection at screening (or who have a known history of hepatitis B infection), this protocol will now require monthly monitoring for potential hepatitis B reactivation. The reason for this amendment is hepatitis B reactivation has occurred in patients treated with Btk inhibitors including 1 subject receiving ACP-196 (Ngoma 2015).

Clarifying edits and typographical changes have been made throughout the protocol. In addition, the following substantive changes were made as part of this amendment:

Change	Rationale
In various parts of the protocol, the	The nonproprietary name of acalabrutinib
nonproprietary name for ACP-196 was	was recently approved for use.
introduced.	
Title Page	Administrative change
Sponsor address changed from:	
[name]	
The Netherlands	
to new address of:	
[name]	
[name]	
I ne Netherlands	
Synoneie	To ansure consistency between the body
Synopsis	of the protocol and the synopsis
Lindated to reflect changes made	of the protocol and the synopsis.
throughout the protocol	
Section 3.4.2 Evolucion Critoria	As hapatitis B virus (HB)() reactivation
Pavised text as follows (bold is now	As nepatities of virus (Hov) reactivation
toxt):	treatment this evaluation criterion was
11 Known history of human	further clarified to state that subjects who
immunodeficiency virus (HIV)	are henatitis B core antibody positive who
serologic status reflecting active	are surface antigen negative or who are
hepatitis B or C infection. or any	hepatitis C antibody positive will need to
uncontrolled active systemic infection.	have a negative PCR result before
Subjects with hepatitis B core	enrolling, and subjects who are hepatitis
antibody positive who are surface	B surface antigen positive or hepatitis B
antigen negative or who are hepatitis	PCR positive, and those who are hepatitis
C antibody positive will need to have a	C PCR positive are excluded from the
negative polymerase chain reaction	study.

Change	Rationale
(PCR) result before enrollment. Those	
who are hepatitis B surface antigen positive or hepatitis B PCR positive and those who are hepatitis C PCR positive will be excludedKnown history of human immunodeficiency virus (HIV) or active infection with hepatitis C virus (HCV) or hepatitis B virus (HBV) or any uncontrolled active systemic infection.	
Section 3.7.2 Hepatitis B Virus	As HBV reactivation has occurred in
Reactivation New section and corresponding language was added:	1 subject on ACP-196 treatment, this language is being added to ensure adequate monitoring of patients who are anti-HBc positive or with a history of HBV.
Serious or life-threatening reactivation	, ,
of viral hepatitis may occur in subjects treated with ACP-196. Therefore, subjects who are hepatitis B core antibody (anti-HBc) positive, or have a known history of hepatitis B virus (HBV) infection, should be monitored monthly with a quantitative PCR test for HBV DNA. Monthly monitoring should continue until 12 months after last dose of ACP-196. Any subject with a rising viral load (above lower limit of detection) should discontinue ACP-196 and have antiviral therapy instituted and a consultation with a physician with expertise in managing hepatitis B. Insufficient data exist regarding the safety of resuming ACP-196 in subjects who develop HBV reactivation.	Subsequent sections were renumbered accordingly.
Section 4.1.16 Hepatitis B and C Testing	
New section and corresponding language was added:	
Hepatitis serology testing must include hepatitis B surface antigen (HBsAg), hepatitis B surface antibody (HBsAb), anti-HBc, and hepatitis C (HCV) antibody. Since intravenous immunoglobulins (IVIG) may cause false positive hepatitis serology, subjects who are receiving prophylactic IVIG and have positive	

Acerta Pharma

Change	Rationale
HBsAg or anti-HBc must have negative hepatitis B DNA to be eligible. In addition, any subjects testing positive for any hepatitis serology, must have PCR testing (see Appendix 5 and exclusion criterion #11). Testing will be done by local or central laboratory. Refer to Section 3.7.2 and Appendix 5 regarding monitoring of subjects who are anti-HBc positive or have a known history of HBV	
Appendix 5. Schedule of	Revised to be consistent with this
Assessments The schedule of assessments and	amendment.
footnotes were revised, as appropriate, to	
match the body of the protocol as	
described above regarding nepatitis	
HBV PCR testing.	

TABLE OF CONTENTS

1.0	BACK	ROUND INFORMATION	19
1.1	Role of	Btk in Lymphoid Cancers	19
1.2	Preclini	cal Studies	20
	1.2.1	Chemistry	20
	1.2.2	Efficacy Pharmacology	21
	1.2.3	ACP-196 and Thrombus Formation	22
	1.2.4	Safety Pharmacology	23
	1.2.5	Drug-drug Interaction Potential	24
	1.2.6	In Vivo General Toxicology	25
1.3	Clinical	Experience	25

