- 11. Known history of human immunodeficiency virus (HIV), serologic status reflecting active hepatitis B or C infection, or any uncontrolled active systemic infection. Subjects with hepatitis B core antibody positive who are surface antigen negative or who are hepatitis C antibody positive will need to have a negative PCR result before enrollment. Those who are hepatitis B surface antigen positive or hepatitis B PCR positive and those who are hepatitis C PCR positive will be excluded.
- 12. Major surgery within 4 weeks before first dose of ACP-196.
- 13. Known history of a bleeding diathesis (eg, hemophilia, von Willebrand disease)
- 14. History of stroke or intracranial hemorrhage within 6 months before the first dose of ACP-196.
- 15. Requires or receiving anti-coagulation with warfarin or equivalent vitamin K antagonist (eg, phenprocoumon) within 28 days of first dose of study drug.
- 16. Requires treatment with long-acting proton pump inhibitors (eg, omeprazole, esomeprazole, lansoprazole, dexlansoprazole, rabeprazole, or pantoprazole).
- 17. ANC < 0.75 x 10^{9} /L or platelet count < 50 x 10^{9} /L. For subjects with >50% marrow involvement with plasma cells, ANC < 0.50 x 10^{9} /L or platelet count < 30 x 10^{9} /L.
- Creatinine > 2.5 x institutional upper limit of normal (ULN); total bilirubin
 > 2.5 x ULN; and aspartate aminotransferase (AST) or alanine aminotransferase (ALT) > 3.0 x ULN.
- 19. Breastfeeding or pregnant.

20. Concurrent participation in another therapeutic clinical trial.

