3.7.2 Hepatitis B Virus Reactivation

Serious or life-threatening reactivation of viral hepatitis may occur in subjects treated with ACP-196. Therefore, subjects who are hepatitis B core antibody (anti-HBc) positive, or have a known history of hepatitis B virus (HBV) infection, should be monitored monthly with a quantitative PCR test for HBV DNA. Monthly monitoring should continue until 12 months after last dose of ACP-196. Any subject with a rising viral load (above lower limit of detection) should discontinue ACP-196 and have antiviral

therapy instituted and a consultation with a physician with expertise in managing hepatitis B. Insufficient data exist regarding the safety of resuming ACP-196 in subjects who develop HBV reactivation.

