4.1.16 Hepatitis B and C Testing

Hepatitis serology testing must include hepatitis B surface antigen (HBsAg), hepatitis B surface antibody (HBsAb), anti-HBc, and hepatitis C (HCV) antibody. Since intravenous immunoglobulins (IVIG) may cause false positive hepatitis serology, subjects who are receiving prophylactic IVIG and have positive HBsAg or anti-HBc must have negative hepatitis B DNA to be eligible. In addition, any subjects testing positive for any hepatitis serology, must have PCR testing (see Appendix 5 and exclusion criterion #11). Testing will be done by local or central laboratory.

Refer to Section 3.7.2 and Appendix 5 regarding monitoring of subjects who are anti-HBc positive or have a known history of HBV.

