Appendix 5. Schedule of Assessments

	Screenina ^a		0	ycle 1			с У	cle 2	Cvcle 3	Cvcle 4	Cvcles 5-12 ^b	ET/Safety Follow Up ^c
			Da	lys (±	2)		Day	's (± 2)	Days (± 2)	Days (± 2)	Days (± 2)	-
		-	8	15	22	28	15	28	28	28	28	
Informed consent	×											
Confirm eligibility	×											
Medical history	×											
PE ^d /Vital signs ^e /Weight	×	×	×	х	×	×	×	×	×	×	×	×
ECOG status	×	×	×	×	×	×	×	×	×	×	×	×
ECG	×	×										×
Lab assessments:												
Urine pregnancy test ^g	×											×
Hematology ^h	х	х ^q	×	Х	х	×	×	Х	×	×	Х	×
Serum chemistry	×	×d	×	×	Х	×	×	Х	×	×	X	×
Urinalysis ⁱ	х					Х		х	×	×	Every 2 mos	
T/B/NK cell count ^k		Х ^q	×	Х		×		Х			Every 6 mos	
Disease markers	х			Х		×		Х	×	×	Every 2 mos	X
Bone marrow									As	As		
(aspirate/biopsy)									clinically	clinically	As clinically	
/Skeletal survey ^p	×								indicated	indicated	indicated or	
									or to	or to	to contirm a	
									contirm a CR	confirm a CR	CK	
Hepatitis serology ^r	х											
HBV PCR ^s						×		Х	×	х	QM	QM
Pharmacodynamics		ж	ж			۳X		чх				×
Pharmacokinetics ^o		Х	х	Х	×	×						
ACP-196/												
dexamethasone		×	×	×	×	×	×	×	×	×	×	
dispensed												
Study drug compliance		×	х	х	×	×	×	Х	×	х	×	
Tumor assessment ^p	х					×		Х	×	х	×	
Concomitant	×	×	×	×	×	×	×	×	×	×	×	×
Adverse events		×	×	×	×	×	×	×	×	×	×	×

Abbreviations: anti-HBc = hepatitis B core antibody; CR = complete remission; ECG = electrocardiogram; ECOG = Eastern Cooperative Oncology Group; ET = early termination; HBsAb = hepatitis B surface antibody; HBsAg = hepatitis B surface antigen; HBV = hepatitis B virus; HCV = hepatitis C virus; Ig = immunoglobulin; IVIG = intravenous immunoglobulins; mos = months; PCR = polymerase chain reaction; PE = physical exam; QM = every month

Footnotes for ACE-MY-001 Schedule of Study Activities:

- Screening tests should be performed within 21 days before the first administration of study drug, unless otherwise indicated. а.
- Any subjects who have not progressed while receiving study drug treatment, may be eligible to enroll into a long-term follow up study and continue to receive ACPþ.
- An early termination visit is required for any subjects who permanently discontinue study drug early for any reason including disease progression. A 30-day (± 7 days) safety follow-up visit is required when subjects discontinue study drug unless they start another anticancer therapy within that timeframe. ن.

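### In the readable Amendment 2 text, hepatitis serology is scheduled at Screening only; unless Appendix 5 footnotes r and s say otherwise, earlier enrollees with unrecognised anti-HBc positivity would not be found for Section 3.7.2 monitoring

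*Protocol*

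**What the plan says.** **Who is monitored.** Protocol Section 3.7.2 states that "subjects who are hepatitis B core antibody (anti-HBc) positive, or have a known history of hepatitis B virus (HBV) infection, should be monitored monthly" by quantitative HBV DNA PCR, until 12 months after the last dose. A rising viral load is the trigger for stopping ACP-196 and starting antiviral therapy. The Amendment 2 summary gives the reason: "this language is being added to ensure adequate monitoring of patients who are anti-HBc positive or with a history of HBV".

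**When serology is done.** The summary of Amendment 2 says "This protocol is being amended to add hepatitis serology testing at screening". Under Section 3.4.2, criterion 11, subjects who are anti-HBc positive and HBsAg negative "will need to have a negative PCR result before enrollment". Section 4.1.16 lists the markers (HBsAg, HBsAb, anti-HBc, HCV antibody) and adds that "any subjects testing positive for any hepatitis serology, must have PCR testing", but sets no time point for subjects already being dosed. In the Appendix 5 grid the row "Hepatitis serology" (footnote r) has one mark, under Screening. The HBV PCR row (footnote s) starts at Cycle 1 Day 28.

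**What is new.** For both 3.7.2 and 4.1.16 the summary records "New section and corresponding language was added". For Appendix 5 it says the schedule and its "footnotes were revised, as appropriate, to" match the body of the protocol.

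**The concern.** The monitoring duty in 3.7.2 depends on knowing who is anti-HBc positive. Without a known history, only serology can show that. If serology is done only at Screening, and the requirement arrived partway through the trial, sites have no instruction to look for anti-HBc among subjects already past Screening.

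The amendment was prompted by HBV reactivation on Btk inhibitors, including 1 subject on ACP-196, and 3.7.2 describes the event as potentially serious or life-threatening. The risk does not depend on the protocol version under which a subject enrolled. Section 3.8 lets subjects stay on drug indefinitely while they benefit, subject to withdrawal for definitive progression. A subject not known to be anti-HBc positive would have no viral load measured, so the 3.7.2 trigger could not fire.

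Safety is the primary objective, so reporting is touched as well. SAP Section 10.6.2 plans a listing of subjects with any hepatitis B test. An earlier enrollee missing from that listing may simply not have been tested.

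**Working it through.** The plan states no figure to reproduce. The check compares texts and counts schedule columns.

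1. **Entry routes to monitoring (3.7.2).** There are two: anti-HBc positive, or known HBV history. Neither is limited by enrollment date or protocol version.

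2. **How each route is detected.** Known history comes from the medical history (4.1.2). Anti-HBc status in someone without a known history comes only from serology.

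3. **Where serology sits in the current text.** Criterion 11 acts before enrollment, and 4.1.16 gives content but no timing. The Appendix 5 visit columns are Screening (1), Cycle 1 Days 1, 8, 15, 22 and 28 (5), Cycle 2 Days 15 and 28 (2), Cycle 3 (1), Cycle 4 (1), Cycles 5-12 (1) and ET/Safety Follow Up (1): 1 + 5 + 2 + 1 + 1 + 1 + 1 = 12.

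| Row | Columns marked | Where |
|---|---|---|
| Hepatitis serology | 1 of 12 | Screening |
| HBV PCR | 6 of 12 | Cycle 1 Day 28, Cycle 2 Day 28, Cycle 3, Cycle 4, Cycles 5-12, ET/Safety Follow Up |
| Hematology | 12 of 12 | all |
| Serum chemistry | 12 of 12 | all |

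4. **What earlier enrollees had.** The original protocol (11 July 2014; 3.4.2, criterion 10) and Amendment 1 (20 March 2015; 3.4.2, criterion 11) excluded known HIV history or active HCV or HBV infection. Neither has a hepatitis testing subsection in 4.1 or a serology row in its schedule.

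5. **Combining 1 to 4.** An earlier enrollee with a known HBV history enters monitoring by the second route. One who is anti-HBc positive without a known history can enter only by the first, and nothing in the readable text orders the test.

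6. **Timing.** Amendment 2 is dated 13 January 2016. SAP Section 3.1 says enrollment stopped by memo of 15 March 2016. The interval is 18 + 29 + 15 = 62 days, so new-subject screening under Amendment 2 lasted at most 62 days. The stop came after the amendment and is no criticism of it. The documents do not say how many subjects enrolled under each version.

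7. **Ceiling on the remedy.** Hematology and chemistry are scheduled at every visit, so a draw is already available. With 40 planned subjects and two markers each, 40 × 2 = 80 marker results at most, plus any replacements under 3.4.3. This ceiling counts all planned subjects, so it bounds cost and does not estimate who is affected.

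**The case against.** The strongest objection is that the decisive text could not be read. Footnotes r and s attach to exactly the two rows at issue, and 4.1.16 sends the reader to Appendix 5 for both PCR testing and monitoring. The appendix's abbreviation list defines anti-HBc, HBsAb, HBsAg, HCV and IVIG, which the grid and readable footnotes do not use, so the unread footnotes probably have real content. Footnote s could also widen the PCR row beyond the 3.7.2 group. This stands: a gap is not proven. What weighs the other way is that the Amendment 2 list of substantive changes names no catch-up test, the footnotes are said to follow the body, and those abbreviations are all terms already used in 4.1.16. I think silence more likely, but that is an inference.

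A second objection is that the screening-only phrase comes from an amendment summary, and a mismatch between a summary and current text is not an error. That is correct, but the point rests on the current grid, 4.1.16 and 3.7.2; the summary only agrees with them.

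A third is that the residual group is narrow and partly protected. Active HBV infection was always excluded, and known history is covered. ALT, AST and bilirubin are measured at every scheduled visit, 4.0 allows extra tests if clinically indicated, and 7.9 requires ongoing subjects to be informed and re-consented if a change increases risk. All of this stands and limits the size of the concern. None of it is systematic serology, and none supplies the viral load on which 3.7.2 acts.

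**Conclusion.** The point holds as a conditional one. In the readable text, 3.7.2 covers all anti-HBc positive subjects, serology is scheduled once at Screening, and no provision identifies earlier enrollees with unrecognised anti-HBc positivity who are still on ACP-196. It rests on one assumption: that footnotes r and s do not supply a catch-up test. If they do, the point falls away.

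A reader might infer that Amendment 2 left earlier enrollees untested, or that subjects were exposed to undetected reactivation. The documents do not support either. The footnotes are unread, and sites could test on clinical grounds. Neither the number of earlier enrollees still on drug nor the anti-HBc prevalence is given. The crossover permission in the March 2016 memo suggests some subjects were still on treatment, without a count. No probability or number affected can be stated.

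Within those limits the matter deserves action, because the event is potentially life-threatening, the remedy is cheap, and the added line does no harm if it proves redundant. Confidence is medium.

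**What to change.** First read Appendix 5 footnotes r and s. If they do not already cover ongoing subjects, add to Section 4.1.16 and Appendix 5:

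> *Subjects already receiving ACP-196 when Amendment 2 takes effect: HBsAg and anti-HBc once, at the next scheduled blood draw; if either is positive, HBV PCR, with monitoring per Section 3.7.2.*

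The reflex PCR only applies the rule already in 4.1.16. The cost is two serology markers per ongoing subject at an existing draw, HBV PCR for positives and any monthly monitoring that follows, and IRB/IEC approval of the added line (with regulatory approval as appropriate) under Section 7.2. No extra visit is needed.

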Figure 1-1.	Effect of ACP-196 (1 µM) and Ibrutinib (1 µM) on Thrombus Formation	23
Figure 1-2.	Kaplan-Meier Curves for Progression-free Survival by Investigator	
Asses	sment for ACE-CL-001 (N=75; excludes Richter's Syndrome Cohort and	
Ibrutin	ib R/R Cohort)	31
Figure 1-3.	Median (95% CI) Change from Baseline in ALC/SPD Over Time	33

ABBREVIATIONS

ACP-196	acalabrutinib
AE(s)	adverse event(s)
ALT	alanine aminotransferase
ANC	absolute neutrophil count
anti-HBc	hepatitis B core antibody
AST	aspartate aminotransferase
AUC	area under the curve
BCR	B-cell receptor
BID	twice a day (dosing)
Btk	Bruton tyrosine kinase
BUN	blood urea nitrogen
CBC	complete blood count
CFR	Code of Federal Regulations
cGMP	current Good Manufacturing Practices
CLL	chronic lymphocytic leukemia
C _{max}	maximum concentration
CR	complete remission (response)
CSSF	Clinical Supplies Shipping Receipt Form
СТ	computed tomography
CTCAE	Common Terminology Criteria for Adverse Events
CYP	cytochrome P450
DLBCL	diffuse large B-cell lymphoma
DLT	dose-limiting toxicity
ECG	electrocardiogram
ECOG	Eastern Cooperative Oncology Group
eCRF	electronic case report form
EGFR	epidermal growth factor receptor
FDA	Food and Drug Administration
FIH	first-in-human (trial)
FLC	(serum) free light chains
GCP	Good Clinical Practice
GLP	Good Laboratory Practices
HBsAb	hepatitis B surface antibody

HBsAg	hepatitis B surface antigen
HBV	hepatitis B virus
HCV	hepatitis C virus
hERG	human ether-à-go-go-related gene
HIV	human immunodeficiency virus
HNSTD	highest nonseverely toxic dose
ICF	informed consent form
IEC	Independent Ethics Committee
IFE	immunofixation electrophoresis
lg	immunoglobulin
IRB	Institutional Review Board
IVIG	intravenous immunoglobulins
LDH	lactate dehydrogenase
MCL	mantle cell lymphoma
MedDRA	Medical Dictionary for Regulatory Activities
MM	multiple myeloma
MR	minimal response
NHL	non-Hodgkin lymphoma
NK	natural killer (cells)
ORR	overall response rate
PBMC(s)	peripheral blood mononuclear cells
PCR	polymerase chain reaction
PD	pharmacodynamics
PI3K	phosphoinositide-3 kinase
PK	pharmacokinetics
PR	partial remission (response)
QD	once a day (dosing)
QM	every month
QTc	corrected QT interval
SAE(s)	serious adverse event(s)
SD	stable disease
SFLC	serum free light chains
SIFE	serum immunofixation electrophoresis
SPD	sum of the products of the perpendicular diameters (of lymph nodes)
SPEP	serum protein electrophoresis

SUSAR	Suspected Unexpected Serious Adverse Reaction (report)
T _{max}	time to maximum drug concentration
UIFE	urine immunofixation electrophoresis
ULN	upper limit of normal
UPEP	urine serum protein electrophoresis
VGPR	very good partial response
WHO	World Health Organization

Protocol Number:	ACE-MY-001		
Study Drug:	ACP-196 (acalabrutinib)		
Protocol Title:	An Open-label, Phase 1b Study of ACP-196 in Subjects with Multiple Myeloma		
Phase:	Phase 1b		
Comparator:	None		
Background and Rationale for Study	Clinical studies have shown that targeting the B-cell receptor (BCR) signaling pathway by inhibiting Bruton tyrosine kinase (Btk) produces significant clinical benefit in patients with non-Hodgkin lymphoma (NHL) and chronic lymphocytic leukemia (CLL). Preclinical studies have shown that Btk inhibition significantly reduces in vivo multiple myeloma (MM) cell growth and MM cell- induced osteolysis in a murine model (Tai 2012). Data on the utility of Btk targeted therapy in patients with MM is very preliminary, but suggests there are subsets of patients with malignant plasma cell clones in which Btk is active as evidenced by expression of phosphorylated Btk (p-Btk), and that these cancers may be particularly responsive to Btk inhibitor therapy. Acerta Pharma BV (Acerta Pharma) has developed a novel second generation Btk inhibitor, ACP-196, that achieves significant oral bioavailability and potency in preclinical models. ACP-196 monotherapy is currently in multiple Phase 1/2 studies in subjects with chronic lymphocytic leukemia (CLL) and other indications. The purpose of this study is to evaluate the safety, pharmacokinetics (PK), pharmacodynamics (PD), and activity of		
	subjects with relapsed MM. The study will explore the concept of whether biomarkers may help identify patients with MM that are particularly likely to benefit from Btk inhibitor therapy.		
Study Design:	This study is a multicenter, open-label, randomized, parallel-group study to be conducted at approximately 20 sites in 2 countries (United Kingdom and United States). Forty subjects will be equally randomized (1:1 ratio) into 2 cohorts to receive ACP-196, with and without dexamethasone:		
	 Cohort 1: ACP-196 100 mg twice per day (BID) continuously Cohort 2: ACP-196 100 mg BID continuously and dexamethasone 40 mg once weekly 		
	Twenty-eight days of study drug administration is 1 cycle. Treatment may be continued for > 28 days until disease		

STUDY SYNOPSIS

	progression or an unacceptable drug-related toxicity occurs. For subjects in Cohort 1, if documented disease progression occurs, then dexamethasone can be added to the treatment regimen. Additional dose modification provisions are provided in the study protocol. Note: temporary withholding of study drug for as little as 7 days can cause a transient worsening of disease and/or of constitutional symptoms. Refer to Section 3.8 for more information on assessing disease progression under these circumstances. All subjects who discontinue study drug will have a safety follow-up visit 30 (±7) days after the last dose of study drug unless they have started another cancer therapy within that timeframe.					
	All subjects will have hematology, chemistry, and urinalysis safety panels done at screening. Once dosing commences (Day 1), all subjects will be evaluated for safety, including serum chemistry and hematology, once weekly for the first 4 weeks, every 2 weeks in Cycle 2 and monthly thereafter. PK/PD testing will be done in Cycle 1 and Cycle 2. Tumor assessments will be done at 8- to 12-week intervals during the trial.					
	Refer to Appendix 5 for a comprehensive list of study assessments and their timing. The end of trial is defined as the point when the last subject on the study exits the study for any reason.					
Study Objectives:	Primary Objective:					
	• To characterize the safety profile of ACP-196 with and without dexamethasone in subjects with relapsed or refractory MM					
	Secondary Objectives:					
	• To characterize the PK profile of ACP-196 with and without dexamethasone and the PK profile of dexamethasone with concomitant ACP-196 administration					
	To evaluate the PD effects of ACP-196 with and without dexamethasone					
	• To evaluate the activity of ACP-196 with and without dexamethasone as measured by overall response rate, duration of response, clinical benefit rate, disease control rate, and progression-free survival					
	To explore the relationship between biological markers in MM cells and response to therapy					
Safety Parameters:	Type, frequency, severity, timing of onset, duration, and relationship to study drug (ie, ACP-196, dexamethasone, or both) of any adverse events (AEs) or abnormalities of laboratory tests; serious adverse events (SAEs); or AEs leading to discontinuation of study treatment.					

Efficacy Parameters:	Overall response rate (ORR)				
	Duration of response				
	Clinical benefit rate				
	Disease control rate				
	Progression-free survival				
Pharmacokinetic Parameters:	The plasma PK of ACP-196 will be characterized using noncompartmental analysis. The following PK parameters will be calculated, whenever possible, from plasma concentrations of analytes:				
	 AUC_{0-t}: Area under the plasma concentration-time curve calculated using linear trapezoidal summation from time 0 to time t, where t is the time of the last measurable concentration (C_t). 				
	• AUC ₀₋₁₂ : Area under the plasma concentration-time curve from 0 to 12 hours, calculated using linear trapezoidal summation.				
	• AUC _{0-∞} : Area under the plasma concentration-time curve from 0 to infinity, calculated using the formula: AUC _{0-∞} = AUC _{0-t} + C_t / λ_z , where λ_z is the apparent terminal elimination rate constant.				
	• AUC _{0-24calc} : Area under the plasma concentration-time curve from 0 to 24 hours, calculated by doubling the value for AUC ₀₋₁₂ .				
	C _{max} : Maximum observed plasma concentration				
	• T _{max} : Time of the maximum plasma concentration (obtained without interpolation)				
	 t_{1/2}: Terminal elimination half-life (whenever possible) 				
	 λ_z: Terminal elimination rate constant (whenever possible) CL/F: Oral clearance 				
Pharmacodynamic Parameters:	The occupancy of Btk by ACP-196 will be measured in peripheral blood mononuclear cells (PBMCs) and in bone marrow, when available, with the aid of a biotin-tagged ACP-196 analogue probe. The effect of ACP-196 on biologic markers of B-cell function will also be evaluated.				
Sample Size:	Forty subjects with 20 subjects in each cohort.				
Inclusion Criteria:	 Men and women ≥ 18 years of age. 				
	• A confirmed diagnosis of MM, which has relapsed after, or been refractory to ≥ 1 prior therapy for MM, and is progressing at the time of study entry.				
	• Evaluable myeloma at screening, defined as the presence of at least one of the following:				
	 Serum M-protein ≥ 0.5 g/dL 				
	◦ Urine M-protein ≥ 200 mg/24 hours				

		 In subjects without detectable serum or urine M-protein, serum free light chain (SFLC) > 100 mg/L (involved light chain) and an abnormal serum kappa/lambda ratio
		 For subjects whose disease can only be reliably measured by serum quantitative immunoglobulin A (IgA), IgA ≥ 750 mg/dL (0.75 g/dL)
	•	Eastern Cooperative Oncology Group (ECOG) performance status of ≤ 2 .
	•	Agreement to use acceptable methods of contraception during the study and for 30 days after the last dose of study drug if sexually active and able to bear or beget children.
	•	Agreement to refrain from sperm donation during the study and for 30 days after the last dose of study drug.
	•	Willing and able to participate in all required evaluations and procedures in this study protocol including swallowing capsules without difficulty.
	•	Ability to understand the purpose and risks of the study and provide signed and dated informed consent and authorization to use protected health information (in accordance with national and local patient privacy regulations).
Exclusion Criteria:	•	Plasma cell leukemia or circulating plasma cells ≥ 2 x 10 ⁹ /L
	•	Prior malignancy, except for adequately treated basal cell or squamous cell skin cancer, in situ cervical cancer, or other cancer from which the subject has been disease free for ≥ 2 years or which will not limit survival to < 2 years. Note: these cases must be discussed with the Medical Monitor.
	•	A life-threatening illness, medical condition, or organ system dysfunction which, in the investigator's opinion, could compromise the subject's safety, interfere with the absorption or metabolism of ACP-196, or put the study outcomes at undue risk.
	•	Significant cardiovascular disease such as uncontrolled or symptomatic arrhythmias, congestive heart failure, or myocardial infarction within 6 months of screening, or any Class 3 or 4 cardiac disease as defined by the New York Heart Association Functional Classification, or QTc > 480 msec.
	•	Malabsorption syndrome, disease significantly affecting gastrointestinal function, or resection of the stomach or small bowel, gastric bypass, symptomatic inflammatory bowel disease, or partial or complete bowel obstruction.
	•	Any immunotherapy within 4 weeks of first dose of study drug.
	•	The time from the last dose of the most recent chemotherapy or experimental therapy to the first dose of study drug is < 5 times the half-life of the previously administered agent(s).
	•	Prior exposure to a B-cell receptor (BCR) inhibitor (eg, Btk, phosphoinositide-3 kinase [PI3K], or Syk inhibitors) or BCL-2 inhibitors (eg, ABT-199).

 Ongoing immunosuppressive therapy, including systemic or enteric corticosteroids for treatment of MM or other conditions. Note: Subjects may use topical or inhaled corticosteroids as therapy for comorbid conditions. During study participation, subjects may receive systemic or enteric corticosteroids as needed for MM therapy or treatment-emergent comorbid conditions. Grade ≥ 2 toxicity (other than alopecia) continuing from prior 		
anticancer therapy including radiation.		
 Known history of human immunodeficiency virus (HIV), serologic status reflecting active hepatitis B or C infection, or any uncontrolled active systemic infection. Subjects with hepatitis B core antibody positive who are surface antigen negative or who are hepatitis C antibody positive will need to have a negative polymerase chain reaction (PCR) result before enrollment. Those who are hepatitis B surface antigen positive or hepatitis B PCR positive and those who are hepatitis C PCR positive will be excluded. 		
 Major surgery within 4 weeks before first dose of ACP-196. 		
 Known history of a bleeding diathesis (eg, hemophilia, von Willebrand disease) 		
 History of stroke or intracranial hemorrhage within 6 months before the first dose of ACP-196. 		
 Requires or receiving anti-coagulation with warfarin or equivalent vitamin K antagonist (eg, phenprocoumon) within 28 days of first dose of study drug. 		
• Requires treatment with long-acting proton pump inhibitors (eg, omeprazole, esomeprazole, lansoprazole, dexlansoprazole, rabeprazole, or pantoprazole)		
 ANC < 0.75 x 10⁹/L or platelet count < 50 x 10⁹/L. For subjects with > 50% plasma cells in the marrow, ANC < 0.50 x 10⁹/L or platelet count < 30 x 10⁹/L. 		
 Creatinine > 2.5 x institutional upper limit of normal (ULN); total bilirubin > 2.5 x ULN; or aspartate aminotransferase (AST) or alanine aminotransferase (ALT) > 3.0 x ULN. 		
Breastfeeding or pregnant.		
Concurrent participation in another therapeutic clinical trial.		
ACP-196 is provided as 100-mg hard gelatin capsules prepared using standard pharmaceutical grade excipients.		
ACP-196 is an orally administered product. ACP-196 can be administered with or without food.		
Regimens:		
 Cohort 1 (BID): 100 mg ACP-196 (1 x 100-mg capsule) administered 12 hours apart (BID dosing = 200-mg total daily dose) 		

	 Cohort 2 (BID + dexamethasone): 100 mg ACP-196 (1 x 100-mg capsule) administered 12 hours apart (BID dosing = 200-mg total daily dose) plus 40 mg dexamethasone administered once weekly (weekly dosing = 40-mg total weekly dose)
Concomitant Medications:	The effect of agents that reduce gastric acidity (eg, proton pump inhibitors, H2-receptor antagonists, or antacids) on ACP-196 absorption is currently being evaluated in a healthy volunteer study (ACE-HV-004). Preliminary results from this study suggest subjects should avoid the use of calcium carbonate containing drugs or supplements (eg, antacids or calcium supplements) and short-acting H2-receptor antagonists for a period of at least 2 hours before and after taking ACP-196. Use of omeprazole or esomeprazole or any other long-acting proton pump inhibitors while taking ACP-196 is not permitted due to a potential decrease in study drug exposure; however, if a subject requires treatment with a long-acting proton pump inhibitor while on study (eg, to treat an ulcer), treatment options should be discussed with the Medical Monitor. Concomitant use of strong inhibitors/inducers of CYP3A should be avoided when possible. If a subject requires a strong CYP3A inhibitor while on study, monitor the subject closely for potential toxicities.
Statistics:	Subjects meeting the stated eligibility requirements will be enrolled onto the study. Subjects will be randomized in a 1:1 ratio into the 2 regimens (ACP-196 with and without dexamethasone). With a sample size of 19 subjects per cohort, the power to detect the difference between a null-hypothesis response rate of 15% and an alternative response rate of 40% with a 0.025 one-sided significance level is 0.69 using a one-group, exact binomial test. A sample size of 19 subjects per cohort will also provide a 97.5% one-sided confidence interval centered around an expected ORR of 40% that excludes an ORR of 18.6% as a lower bound. Descriptive statistics (including means, standard deviations, and medians for continuous variables and proportions for discrete variables) will be used to summarize data, as appropriate.

